### 5.3. Lifestyle Considerations

Potential participants must be willing and able to adhere to the following lifestyle restrictions during the course of the study to be eligible for participation:

1. Criterion modified per Amendment 2.
  - 1.1. A woman of childbearing potential who is heterosexually active must remain on a highly effective method of birth control (Inclusion Criterion 14) during the study and after receiving the last administration of study intervention for at least 5 months if participating in Part 1 (due to potential exposure to adalimumab) and for at least 12 weeks if participating in Part 2.
2. A woman must agree not to donate eggs (ova, oocytes) during the study and for a period of at least 12 weeks following the last administration of study intervention.
3. Criterion modified per Amendment 2.
  - 3.1. A man who is sexually active with a female of childbearing potential and has not had a vasectomy must agree to use a barrier method of birth control (See Inclusion Criterion 17) during the study and for at least 12 weeks after receiving the last administration of study intervention.
4. A man must agree to not donate sperm during the study and for at least 12 weeks after receiving the last administration of study intervention.
5. Participants must comply with restrictions on concomitant medications and therapies specified in the protocol (see Section 6.7.5).

6. Participants are required to use a daily antiseptic wash on their HS lesions before randomization and continue the treatment throughout the study (including the safety follow-up period) (see Section 6.7.2).
7. Participants must not receive a live virus or bacterial vaccination during the study and for 3 months after the last administration of any study intervention.
8. Agree to follow all requirements that must be met during the study as noted in the Inclusion and Exclusion Criteria (e.g., contraceptive requirements).
9. It is recommended that participants are up-to-date on age-appropriate vaccinations prior to screening as per routine local medical guidelines. For study participants who received locally-approved (and including emergency use-authorized) COVID-19 vaccines recently prior to study entry, follow applicable local vaccine labelling, guidelines, and standards of care for patients receiving immune-targeted therapy when determining an appropriate interval between vaccination and study enrolment (see also Section 6.7 concomitant medications).

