1.3.1. Screening Through Week 16, Part 1; 1.3.2. Screening Through Week 16, Part 2	
 
Updated time point for medical history/demographics.
 
Updated footnote k for Population PK sample.
 
Removed footnote “s” in Amendment 1 and renumbered the footnotes after it in Amendment 2.
 
	To correct errors.

Section number and Name	Description of Change	Brief Rationale
1.3.1. Screening Through Week 16, Part 1; 1.3.2. Screening Through Week 16, Part 2; 5.1. Inclusion Criteria; 8.2.4. Clinical Safety Laboratory Assessments; 10.3. Appendix 3	Changed “Urine pregnancy test” to “Pregnancy test” in Schedule of Activities and updated IC #15 and Clinical Laboratory Tests to cover both serum and urine pregnancy tests	To correct an error.
1.3.2. Screening Through Week 16, Part 2; 8.1.3. Lesion Counts; 8.1.11. HS Lesion Monitoring Using Medical Infrared Thermography; 10.17. Appendix 17	Reduced collection time points for lesion counts, HS-IGA, and images of skin lesions in Part 2.	To decrease burden for participants while collecting sufficient efficacy data.
1.3.2. Screening through Week 16, Part 2; 10.3. Appendix 3	Added fasting lipid panel to clinical laboratory tests in Part 2.	To further investigate the timing and the magnitude of the possible changes in lipid levels during the course of the current study. A mild elevation of serum triglycerides was observed in some participants in the bermekimab Phase 1 study.
2.2. Background; 11. References	Added 2 references for HiSCR.	References missed in original protocol and Amendment 1.
5.1. Inclusion Criteria; 5.2. Exclusion Criteria	Added IC #22 and EC #43 for BCG vaccination.	To correct an error (missing in original protocol and Amendment 1).
5.2. Exclusion Criteria; 5.3. Lifestyle Considerations	
 
Modified EC #12 to refer to IC #13.
 
Modified Criterion #3 to refer to IC #17.
 
	To correct an error.
5.2. Exclusion Criteria	Added EC #44 for congenital conditions including Down syndrome.	To maintain consistent demographics.
5.3. Lifestyle Considerations	Modified lifestyle consideration #1	To be consistent with the labeling for adalimumab in Part 1.
6.7.1. Rescue Medication	Included the correct formulation of the rescue medication.	To correct an error in dosage form.
6.7.4. Analgesic Therapy	Modified use of NSAIDs.	To provide flexibility in compliance with local labeling recommendations.

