    - Of childbearing potential and practicing a highly effective method of contraception (failure rate of <1% per year when used consistently and correctly) and agrees to remain on a highly effective method while receiving study intervention and until 12 weeks after last dose - the end of relevant systemic exposure. The investigator should evaluate the potential for contraceptive method failure (e.g., noncompliance, recently initiated) in relationship to the first administration of study intervention. Examples of highly effective methods of contraception are located in Section 10.6.
  15. Criterion modified per Amendment 2.
    - 15.1. A woman of childbearing potential must have a negative highly sensitive serum ( $\beta$ -human chorionic gonadotropin [ $\beta$ -hCG]) at screening and a negative urine pregnancy test at Week 0 prior to administration of study intervention.
  16. A woman must agree not to donate eggs (ova, oocytes) for the purposes of assisted reproduction during the study and for at least 12 weeks administration of study intervention.
  17. A man who is sexually active with a woman of childbearing potential and who has not had a vasectomy must agree to use a barrier method of birth control (eg, either a condom [with spermicidal foam/gel/film/cream/suppository if available in their locale] or a partner with an occlusive cap [diaphragm or cervical/vault caps] plus spermicidal foam/gel/film/cream/suppository if available in their locale), during the study and for at least 12 weeks intervention.
  18. All men must also agree to not donate sperm during the study and for at least 12 weeks after receiving the last administration of study intervention.
  19. Be willing and able to adhere to the prohibitions and restrictions specified in this protocol.

20. Must sign an informed consent form (ICF) indicating that he or she understands the purpose of, and procedures required for, the study and is willing to participate in the study.
21. Must sign a separate ICF if he or she agrees to provide an optional DNA sample for research (where local regulations permit) or participate in one of the substudies. Refusal to give consent for the optional DNA research sample does not exclude a participant from participation in the study.
22. Agree not to receive a Bacille Calmette-Guérin (BCG) vaccination during the study, and for 12 months after the last administration of study intervention.

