37. Is pregnant, or breast-feeding, or planning to become pregnant while enrolled in this study or within 12 weeks after the last administration of study intervention.
38. Plans to father a child while enrolled in this study or within 12 weeks after the last administration of study intervention.
39. Is known to have had a substance abuse (drug or alcohol) disorder within the previous 12 months.
40. Lives in an institution on court or authority order.
41. Has any condition for which, in the opinion of the investigator, participation would not be in the best interest of the participant (eg, compromise the well-being) or that could prevent, limit, or confound the protocol-specified assessments.
42. Is an employee of the investigator or study site, with direct involvement in the proposed study or other studies under the direction of that investigator or study site, as well as family members of the employees or the investigator.

43. Has had a BCG vaccination within 12 months of screening.
44. Has congenital conditions including Down syndrome that may impact the clinical course of HS.
45. Has received an anti-TNF drug such as adalimumab within 3 months of the first administration of study intervention. This criterion only applies to participants enrolling in Part 2 of the study. In Part 1, participants previously exposed to adalimumab are excluded.

**NOTE:** Investigators should ensure that all study enrollment criteria have been met at screening. If a participant's clinical status changes (including any available laboratory results or receipt of additional medical records) after screening but before the first administration of study intervention is given such that he or she no longer meets all eligibility criteria, then the participant should be excluded from participation in the study. Section 5.4, Screen Failures, describes options for retesting. The required source documentation to support meeting the enrollment criteria are noted in Section 10.4.

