#### **5.4. Screen Failures**

If, during the screening phase, the subject has not met all inclusion criteria or met any exclusion criteria, or is unable or unwilling to adhere to the prohibitions and restrictions of the study, the subject is considered to be a screen failure and is not eligible to be randomized at that time.

Retesting of abnormal laboratory values that may lead to exclusion will be allowed once. Retesting can occur at an unscheduled visit during the specified screening period of 6 weeks.

Individuals who do not meet the criteria for participation in this study (screen failure) may be rescreened 1 time. Rescreened participants will be assigned a new participant number, undergo the informed consent process, and then start a new screening period.

Completion of screening and randomization procedures within the specified screening window of approximately 6 weeks is required.

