A participant will not be automatically withdrawn from the study if he or she must discontinue treatment before the end of the treatment regimen. Participants who discontinue study intervention but do not terminate study participation will continue to return for protocol-specified procedures and evaluations for approximately 5 weeks following the last administration of study intervention. The procedures and evaluations listed for the Early Termination Visit should also be performed approximately 5 weeks after the last administration of study intervention.

All procedures and evaluations must be conducted prior to a participant's withdrawal of consent.

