#### **8.2.4. Clinical Safety Laboratory Assessments**

Blood samples for serum chemistry and hematology will be collected as noted in Section 10.3. The investigator must review the laboratory results, document this review, and record any clinically relevant changes occurring during the study in the adverse event section of the CRF. The laboratory reports must be filed with the source documents.

The tests that will be performed by the central laboratory unless otherwise specified or approved by the medical monitor are specified in Section 10.3.

Female participants of childbearing potential will undergo a pregnancy test at screening, before each study intervention administration, and at the Week 36 or Early Termination Visit.

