## 10.6. Appendix 6: Contraceptive Guidance

Participants must follow contraceptive measures as outlined in Section 5.1, Inclusion Criteria. Pregnancy information will be collected and reported as noted in Section 8.3.5, Pregnancy and Appendix 3 Adverse Events, Serious Adverse Events, Product Quality Complaints, and Other Safety Reporting: Definitions and Procedures for Recording, Evaluating, Follow-up, and Reporting.

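### Section 5.3 requires 5 months of contraception after the last dose in Part 1, but Inclusion 14 and Exclusion 37 still give 12 weeks for both Parts

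*Protocol*

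**What the plan says.** Three places in the protocol set a period after the last dose for women.

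- **Section 5.3, item 1.1** (marked as modified by Amendment 2). Heterosexually active women of childbearing potential must stay on highly effective contraception "for at least 5 months if participating in Part 1 (due to potential exposure to adalimumab"). For Part 2 the period is at least 12 weeks.
- **Section 5.1, Inclusion 14.** A woman of childbearing potential agrees to remain on a highly effective method during treatment and "until 12 weeks after last dose - the end of relevant systemic exposure". There is no split by Part and no amendment mark.
- **Section 5.2, Exclusion 37.** A woman is excluded if she is "planning to become pregnant while enrolled in this study or within 12 weeks after the last administration of study intervention". Again there is no split and no amendment mark.

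The Amendment 2 summary of changes gives the reason for modifying the first lifestyle item: "To be consistent with the labeling for adalimumab in Part 1". Section 10.6 (Appendix 6) directs sites to one place only: "Participants must follow contraceptive measures as outlined in Section 5.1, Inclusion Criteria".

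**The concern.** Amendment 2 appears to have been carried through only in part. The longer Part 1 period is in the lifestyle section, but the inclusion and exclusion criteria that cover the same matter were left at 12 weeks. Inclusion 14 also justifies 12 weeks as the point where relevant exposure ends. That cannot be right for Part 1 if the same protocol asks for 5 months because of possible adalimumab exposure.

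This is a participant-safety matter, not a statistical one. A site that follows Appendix 6 to Section 5.1 would give Part 1 women the shorter period. Sites could not reserve the longer period for women on adalimumab, because Section 6.3 keeps investigators and participants blinded until the last participant has completed Week 36 and the database is locked. The rule has to cover every woman of childbearing potential in Part 1.

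**Working it through.** **Comparison of the texts**

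| Source | Part 1 | Part 2 |
|---|---|---|
| Section 5.3, item 1.1 | at least 5 months | at least 12 weeks |
| Section 5.1, Inclusion 14 | 12 weeks | 12 weeks |
| Section 5.2, Exclusion 37 (planned pregnancy) | 12 weeks | 12 weeks |

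The three agree for Part 2 and disagree for Part 1. The disagreement is in the operative text, not merely between that text and the change log.

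**Which text governs.** Section 5.3 opens by making its restrictions a condition of eligibility. Inclusion 19 requires adherence to all protocol restrictions, and Section 5.4 makes a screen failure of anyone "unable or unwilling to adhere to the prohibitions and restrictions of the study". The requirements are cumulative, so 5 months meets all three texts and 12 weeks fails item 1.1.

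**Evidence of an incomplete edit.** Where adalimumab mattered, Amendment 2 split other criteria by Part (Inclusion 7.1, Exclusion 19.1, Exclusion 45). It revised Inclusion 15, directly below Inclusion 14, and also edited Appendix 6. Inclusion 14, Exclusion 37 and the Appendix 6 reference to Section 5.1 do not reflect the longer period.

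**Size of the gap.** The protocol states no gap figure to reproduce, so this is unit conversion only.

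- 12 weeks × 7 = 84 days.
- Five consecutive calendar months = 150 to 153 days, depending on the starting month.
- Gap: 150 − 84 = 66 days to 153 − 84 = 69 days; 66/7 = 9.4 weeks and 69/7 = 9.9 weeks.
- Counting a month as 4 weeks: 5 × 28 = 140 days, and 140 − 84 = 56 days (8 weeks).

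**Position against the visit schedule.** The last scheduled dose is at Week 31.

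- The 12-week period ends at 31 + 12 = Week 43.
- The 5-month period ends at 31 + 150/7 = Week 52.4 to 31 + 153/7 = Week 52.9.
- The last scheduled visit is Week 36, which is 36 − 31 = 5 weeks after the last dose. That is 43 − 36 = 7 weeks before the shorter period ends and 16.4 to 16.9 weeks before the longer one ends.

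Section 8.2.4 says women of childbearing potential "will undergo a pregnancy test at screening, before each study intervention administration, and at the Week 36 or Early Termination Visit". Section 7.1 has participants who stop treatment early, but stay in the study, return "for approximately 5 weeks following the last administration of study intervention". No scheduled contact falls between the end of the shorter period and the end of the longer one.

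**Who is affected.** Heterosexually active women of childbearing potential in Part 1. The documents do not give their number. Randomisation is 1:1:1 among about 150 participants, so about 150/3 = 50 participants of either sex are assigned to adalimumab.

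**The case against.** The strongest reply is that the answer is already determinate. Section 5.3 is binding and names Part 1, adalimumab and 5 months. A woman planning pregnancy four months after her last dose passes Exclusion 37, but she cannot commit to item 1.1 and is therefore ineligible. This stands and limits the harm. It does not make the texts agree: correct practice depends on the site noticing that the stricter rule lies outside the section named in Appendix 6.

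Second, Section 2 says that study intervention means bermekimab throughout the protocol, so the exposure remark in Inclusion 14 might be read as applying to bermekimab alone. That reading fails because item 1.1 uses the same term while giving adalimumab as the reason for the longer period, and Section 6.1, to which the definition refers, also describes adalimumab.

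Third, Inclusion 7.1 requires Part 1 participants to be suitable for adalimumab under local labeling, so investigators should be aware of that labeling. This is a fair partial safeguard, but it states no contraception period.

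Fourth, both periods end after Week 36, so that visit is itself a chance to correct a wrong instruction. This is true. What is missing is any scheduled contact after it.

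Finally, the wording of item 1 before Amendment 2 is not in the documents, so exactly what changed is inferred from the amendment mark and the stated labeling reason. The conflict in the current text does not depend on that inference.

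**Conclusion.** The concern holds. For Part 1, Inclusion 14 and Exclusion 37 state a period 66 to 69 days shorter than Section 5.3 item 1.1 on calendar months, or 56 days shorter on 4-week months. On the protocol's own reasoning the shorter period is inadequate for possible adalimumab exposure. It should be corrected as an operative safety rule, although the practical harm is limited because the stricter rule is binding.

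The figures measure a difference between texts, not an expected shortfall in any woman's contraception. The Week 43 and Week 52 to 53 end dates assume a last dose at Week 31. The consent form was not available, so what participants were told is unknown. No sample size, estimand, analysis or error rate is affected.

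**What to change.** 1. Amend Inclusion 14 and Exclusion 37 to give at least 5 months after the last dose for Part 1 and 12 weeks for Part 2, matching Section 5.3 item 1.1.
2. In Inclusion 14, tie the statement that relevant exposure ends at 12 weeks to bermekimab only.
3. Have Appendix 6 cite Section 5.3 as well as Section 5.1.
4. Check that the consent form gives Part 1 women the 5-month period.

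The cost is wording in two criteria and one cross-reference, plus the consent check. No visits, procedures or analyses are added. SAP Section 1 records a decision on 14 October 2022 to terminate the study, so revised criteria now have little value for new enrolment. Because the obligation runs from the last dose, a short clarification to Part 1 sites would serve the same purpose for women already treated.

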#### **5.4. Screen Failures**

If, during the screening phase, the subject has not met all inclusion criteria or met any exclusion criteria, or is unable or unwilling to adhere to the prohibitions and restrictions of the study, the subject is considered to be a screen failure and is not eligible to be randomized at that time.

Retesting of abnormal laboratory values that may lead to exclusion will be allowed once. Retesting can occur at an unscheduled visit during the specified screening period of 6 weeks.

Individuals who do not meet the criteria for participation in this study (screen failure) may be rescreened 1 time. Rescreened participants will be assigned a new participant number, undergo the informed consent process, and then start a new screening period.

Completion of screening and randomization procedures within the specified screening window of approximately 6 weeks is required.

#### **Participant Identification, Enrollment, and Screening Logs**

The investigator agrees to complete a participant identification and enrollment log to permit easy identification of each participant during and after the study. This document will be reviewed by the sponsor study-site contact for completeness.

The participant identification and enrollment log will be treated as confidential and will be filed by the investigator in the study file. To ensure participant confidentiality, no copy will be made. All reports and communications relating to the study will identify participants by participant identification and age at initial informed consent. In cases where the participant is not randomized into the study, the date seen and age at initial informed consent will be used.

## **6. STUDY INTERVENTION AND CONCOMITANT THERAPY**

### **6.1. Study Interventions Administered**

The study intervention presentation to be used in this study is a sterile liquid formulation of 175 mg/mL of bermekimab in a prefilled syringe with an injectable volume of 2.0 mL (350 mg of bermekimab per syringe). Bermekimab will be manufactured and provided under the responsibility of the sponsor. Refer to the IB for a list of excipients.

Placebo will be provided centrally by the sponsor.

Commercially available adalimumab will be provided by the sponsor as a sterile liquid containing 40 mg/0.4 mL per vial for SC injection in a PFS.

#### **Part 1:**

All participants will receive 4 SC injections at the Week 0 visit (either 4 active, 3 active and 1 placebo, 2 active and 2 placebo, 1 active and 3 placebo, or 4 placebo). From Weeks 1 through 31, all participants will receive 3 SC injections at each administration visit (either 3 active, 2 active and 1 placebo, 1 active and 2 placebo, or 3 placebo). Since 4 SC injections at the Week 0 visit and 3 SC injections will be administered at each administration visit thereafter, each SC injection should be given at a different location of the body. Participants randomized to placebo will receive bermekimab 1050 mg beginning at Week 16 and continuing through Week 31.

#### **Group 1: Placebo**

Participants will receive 4 placebo SC injections at Week 0. Participants will receive 3 placebo SC injections at Week 1 and every week thereafter through Week 15. At Week 16, participants will cross over to receive 3 bermekimab 350 mg SC injections weekly through Week 31.

#### **Group 2: Adalimumab**

Participants will receive 4 adalimumab 40 mg SC injections at Week 0. Participants will receive 3 placebo SC injections at Week 1. Participants will receive 2 adalimumab 40 mg SC injections and 1 placebo SC injection at Week 2. Participants will receive 3 placebo SC injections at Week 3. Participants will receive 1 adalimumab 40 mg SC injection and 2 placebo SC injections at Week 4 and every week thereafter through Week 31.

#### **Group 3: Bermekimab 1050 mg SC qw**

Participants will receive 3 bermekimab 350 mg SC injections and 1 placebo SC injection at Week 0. Participants will receive 3 bermekimab 350 mg SC injections at Week 1 and every week thereafter through Week 31.

